9.5.3 Exploratory Analyses

The change from Baseline to Week 16 in the exploratory endpoints measured at scheduled visits, including individual mFSQ subscales, Caregiver Strain Index total score, NPI-Q Nighttime Behavior domain severity and caregiver distress, Geriatric Depression Scale (Short Form), and the VRFCAT (total time to complete, total number of errors, and total number of forced progressions), will be summarized using an MMRM model similar to that described for the primary analysis, except that 1) the Baseline value of the endpoint being analyzed will be included in the model instead of the Baseline mFSQ total score; and 2) VRFCAT is not

assessed at Weeks 2, 8, and 12, thus the model will only include Weeks 4 and 16. Additional exploratory analyses may be conducted on the VRFCAT data to adjust for deficits of cognition.

In addition to the Week 16 timepoint, each of the primary, secondary, and exploratory endpoints will also be assessed at all other timepoints (Weeks 2, 4, 8, and 12) using the MMRM models described in [Sections 9.5.1, 9.5.2, and 9.5.3](#). These additional timepoints will be considered exploratory.

9.5.4 Safety Analyses

Safety results will be summarized using descriptive statistics using the Safety Analysis Set.

9.5.4.1 Adverse Events

All AEs will be classified into standard terminology using the Medical Dictionary for Regulatory Activities (MedDRA). All AEs will be listed.

A TEAE is defined as an AE that started after the first administration of study drug and no later than the last administration of study drug plus 30 days. All TEAEs, TEAEs leading to discontinuation, TEAEs related to study drug, TEAEs by maximum severity, fatal TEAEs, serious TEAEs, and serious TEAEs related to study drug will all be summarized by system organ class and preferred term.

9.5.4.2 Other Safety Assessments

In addition to the AE reporting described in [Section 7.4](#), the overall safety and tolerability of study drug will be assessed throughout the study by evaluating the following safety variables:

- Measurements or rating scores and change from Baseline values at scheduled timepoints for:
 - Clinical laboratory test results (including hematology, serum chemistry, and urinalysis with continuous results)
 - Vital sign measurements
 - Height, weight, and BMI
 - 12-lead ECG parameters
- Subject counts and percentages for:
 - Abnormal physical examination findings
 - Urinalysis with categorical results

- Categorical analysis for QTc prolongation in accordance with ICH E14 Guidance Document
- Subject counts and percentages for potentially clinically significant (criteria will be specified in the SAP) findings on:
 - Clinical laboratory test results (to include hematology, serum chemistry, and urinalysis)
 - Vital sign measurements
 - 12-lead ECG parameters
- Subject counts and percentages with suicidal ideation or suicidal behavior during the study as assessed by the C-SSRS

Descriptive statistics for continuous results from clinical laboratory tests, vital signs, ECG, height, body weight, and BMI, including changes from Baseline, will be tabulated by timepoint.

For categorical variables, excluding C-SSRS, the frequency distribution (i.e., number and percentage of subjects for each category) will be summarized by timepoint.

For C-SSRS assessment, descriptive statistics for the incidence of subjects with suicidal ideation, suicidal behavior, or suicidality (either ideation or behavior) during the study will be tabulated.

The number and percentage of subjects with PCI post-Baseline values will be summarized at each post-Baseline visit and overall post Baseline for selected parameters. The PCI criteria will be specified in the statistical analysis plan.

9.5.4.3 Exposure to Study Drug

For each subject, the duration of exposure to study drug will be calculated as the number of days from first dose date to last dose date inclusive. Descriptive statistics will be tabulated. A categorical summary will also be provided using categories defined in the SAP.

9.5.4.4 Adherence and Retention Analyses

The number and percentage of subjects in each analysis set, and the number and percentage of subjects who completed the study or withdrew early will be summarized descriptively. A tabulation of the corresponding reasons for early withdrawal from the study will also be provided.

9.5.4.5 Demographics and Other Analyses

Subject demographics and other characteristics, including medical and disease history, will be summarized using descriptive statistics.

In addition, the use of concomitant medications will be summarized by therapeutic class using subject counts and percentages. Concomitant medications will include all medications taken between the first dose date and the last dose date of study drug, inclusive. Concomitant medications will be summarized by anatomical therapeutic chemical (ATC) Level 3 classification and World Health Organization (WHO) Drug Dictionary preferred term.

9.5.5 Subgroup Analyses

Selected subgroup analyses may be performed. Additional details will be provided in the SAP.

9.6 Interim Analyses

An efficacy analysis may be performed when 50% of subjects have completed the study or terminated early. Additional analyses may be performed as necessary throughout the course of the study.

10 STUDY MANAGEMENT AND DATA COLLECTION

10.1 Data Collection and Management Responsibilities

All documents required for the conduct of the study as specified in the ICH GCP guidelines will be maintained by the Investigator in an orderly manner and made available for monitoring and/or auditing by the Sponsor and regulatory authorities.

The Investigator and institution must permit authorized representatives of the Sponsor or designees (including monitors and auditors), regulatory authorities (including inspectors), and the IRB/EC direct access to source documents (such as original medical records). Direct access includes permission to examine, analyze, verify, and reproduce any records and reports that are needed for the evaluation of the study. The Investigator must ensure the reliability and availability of source documents from which the information on the eCRF was derived.

10.2 Source Documents

All study specific information obtained at each study visit must be recorded in the subject's record (source documentation). This data will be entered into a validated electronic data capture (EDC) database by trained site personnel and/or transferred electronically into EDC, as applicable. The source documentation may consist of source notes captured by site personnel as well as laboratory reports, ECG reports, and electronic source data.

10.3 Case Report Forms

Subject data required by this protocol are to be recorded in an EDC system on eCRFs and/or transferred electronically and securely for data review. The Investigator and his or her site personnel will be responsible for completing the eCRFs. The Investigator is responsible for the accuracy and reliability of all the information recorded on the eCRFs. All information requested on the eCRFs needs to be supplied, including subject identification data, visit date(s), assessment values, etc., and any omission or discrepancy will require explanation. All information on eCRFs must be traceable to source documentation (unless the eCRF is considered the source) at the site.

10.4 Confidentiality

The Investigator must ensure that each subject's anonymity is maintained as described below. On the eCRFs or other documents submitted to the Sponsor or designees, subjects must be identified by a subject identification number only. Subject identifiers uniquely identify subjects within the study and do not identify any person specifically. Documents that are not for submission to the Sponsor or designees (e.g., signed ICFs, medical records submitted with SAE reporting) should be kept in strict confidence by the Investigator in compliance with Federal regulations or other applicable laws or ICH guidance on GCP. Data collection and handling should comply with the European Union General Data Protection Regulation (EU GDPR), where applicable. Acadia has assigned a Data Protection Officer (DPO) as per the EU GDPR.

10.5 Study Records Retention

Investigators are required to maintain all essential study documentation as per ICH GCP guidelines. This includes, but is not limited to, copies of signed, dated and completed eCRFs, documentation of eCRF corrections, signed ICFs, audio recordings, subject-related source documentation, and adequate records for the receipt and disposition of all study drug.

Investigators should maintain all essential study documentation, for a period of at least 2 years following the last approval of marketing application in an ICH region (US, Europe, and Japan), or until at least 2 years after the drug investigational program is discontinued, unless a longer period is required by applicable law or regulation. Only the Sponsor can notify an Investigator or vendor when any records may be discarded. Investigators should contact the Sponsor before destroying any files.

10.6 Protocol Exceptions and Deviations

No prospective entry criteria protocol deviations are allowed; all subjects must meet all eligibility criteria in order to participate in the study.

Protocol waivers for eligibility will not be granted by the Sponsor under any circumstances. If, during the course of a subject's post-enrollment participation in the trial it is discovered that the subject did not meet all eligibility criteria, he or she will be discontinued, unless the discontinuation presents an unacceptable medical risk. The justification to allow the subject to continue in the trial will be made by the Sponsor, with medical input from the Investigator, and will be documented. If allowed to remain in the trial, this will be reported as a major protocol deviation and not a waiver. All follow-up safety assessments must be completed and documented as outlined in the protocol ([Section 6.4](#)). The Investigator must report any protocol deviation to the Sponsor and, if required, to the IRB/EC in accordance with local regulations, within reasonable time.

10.7 Protocol Amendments

Changes to the protocol may be made only by the Sponsor (with or without consultation with the Investigator). All protocol modifications must be submitted to the site IRB/EC in accordance with local requirements and, if required, to regulatory authorities, as either an amendment or a notification. Approval for amendments must be awaited before any changes can be implemented, except for changes necessary to eliminate an immediate hazard to trial subjects, or when the changes involve only logistical or administrative aspects of the trial. No approval is required for notifications.

11 QUALITY MANAGEMENT

11.1 Risk Management

The Sponsor utilizes the ICH E6 (GCP) Revision 2 risk management approach that includes methods to assure and control the quality of the trial proportionate to the risks inherent in the trial and the importance of the information collected. The intent is that all aspects of this trial are operationally feasible and that any unnecessary complexity, procedures, and data collection are avoided. The Sponsor's risk management approach includes the following activities:

- Critical Process and Data Identification: during protocol development, risks of processes and data that are critical to ensure human subject protection and the reliability of trial results are identified and assessed.
- Risk Identification: risks to critical trial processes, governing systems, investigational product, trial design, data collection, and recording are identified.
- Risk Evaluation: identified risks are evaluated by considering the following factors: (a) likelihood of occurrence, (b) impact on human subject protection and data integrity, and (c) detectability of errors.

- Risk Control: risks that can be reduced (e.g., mitigating) or can be accepted are differentiated. Risk mitigation activities are incorporated in protocol design and implementation, study plans, training, processes, and other documents governing the oversight and execution of study activities. Where possible, predefined quality tolerance limits are to be defined to identify systematic issues that can impact subject safety or data integrity and deviations from the predefined quality tolerance limits will trigger an evaluation and possibly an action. Contingency plans are developed for issues with a high risk factor that cannot be avoided.
- Periodic risk review, communication, and escalation of risk management activities during trial execution and risk outcome reporting in the clinical study report (CSR).

11.2 Quality Control and Quality Assurance

The Sponsor or designees and regulatory authority inspectors are responsible for contacting and visiting the Investigator for the purpose of inspecting the facilities and, upon request, inspecting the various records of the trial (e.g., eCRFs and other pertinent data) provided that subject confidentiality is respected.

The Sponsor's or designee's monitor is responsible for inspecting the eCRFs at regular intervals throughout the study to verify adherence to the protocol; completeness, accuracy, and consistency of the data; and adherence to local regulations on the conduct of clinical research. The monitor should have access to subject medical records and other study-related records needed to verify the entries on the eCRFs.

The Investigator agrees to cooperate with the monitor to ensure that any problems detected in the course of these monitoring visits are resolved.

In accordance with ICH guidance on GCP and the Sponsor's audit plans, a certain percentage of sites participating in this study will be audited. These audits may include a review of site facilities (e.g., pharmacy, drug storage areas, and laboratories) and review of study-related records may occur in order to evaluate the trial conduct and compliance with the protocol, ICH guidance on GCP, and applicable regulatory requirements.

The Sponsor's or designee's representatives, regulatory authority inspectors and IRB/EC representatives who obtain direct access to source documents should also respect subject confidentiality, taking all reasonable precautions in accordance with applicable regulatory requirements to maintain the confidentiality of subjects' identities.

12 ETHICAL CONSIDERATIONS

12.1 Ethical Standard

The study will be conducted in compliance with the protocol, the Declaration of Helsinki, ICH GCP, and other applicable regulatory requirements (e.g., Serious Breach reporting, urgent safety measures, and EU GDPR).

The study will be performed in accordance with current US Health Insurance Portability and Accountability Act (HIPAA) regulations, US FDA GCP Regulations (US CFR 21 parts 50, 54, 56, and 312), and ICH guidance on GCP (E6) and clinical safety data management (E2A).

In accordance with Directive 75/318/EEC, as amended by Directive 91/507/EEC, the final clinical study report will be signed by an Investigator and/or Coordinating Investigator who will be designated prior to the writing of the clinical study report.

12.2 Institutional Review Board/Ethics Committee

The Investigator or designee will provide the IRB/EC with all requisite material, including a copy of the protocol, informed consent, and any subject information or advertising materials. The study will not be initiated until the IRB/EC provides written approval of the protocol and the informed consent and until approved documents have been obtained by the Investigator and copies received by the Sponsor. All amendments will be sent to the IRB/EC for information (minor amendment) or for submission (major amendment) before implementation. The Investigator will supply the IRB/EC and the Sponsor with appropriate reports on the progress of this study, including any necessary safety updates, in accordance with the applicable government regulations and in agreement with policy established by the Sponsor.

12.3 Informed Consent Process

Properly executed, written informed consent must be obtained from each subject and their study partner/caregiver prior to any screening procedures, including discontinuation of prohibited medications.

The informed consent must, at a minimum, include the elements of consent described in the ICH guidance on GCP and the US CFR 21 part 50.25. A copy of the ICF planned for use will be reviewed by the Sponsor or designee for acceptability and must be submitted by the Investigator or designee together with the protocol, to the appropriate IRB/EC for review and approval prior to the start of the study at that investigational site. Consent forms must be in a language fully comprehensible to the prospective subject. The Investigator must provide the Sponsor or designee with a copy of the IRB/EC letter approving the protocol and the ICF before the study drug supplies will be shipped and the study can be initiated.

The consent form must be revised if new information becomes available during the study that may be relevant to the subject's willingness to continue participation. Any revision must be submitted to the appropriate IRB/EC for review and approval in advance of use.

12.3.1 Consent and Other Informational Documents Provided to Subjects

The subject must be given a copy of the signed informed consent and the original maintained in the designated location at the site.

12.3.2 Consent Procedures and Documentation

It is the Investigator or designee's responsibility to obtain written informed consent from the subject after adequate explanation of the aims, methods, anticipated benefits, and potential hazards of the study. The subject must be given ample time to decide about study participation and opportunity to inquire about details of the study. The IRB/EC-approved consent form must be personally signed and dated by the subject and by the person who conducted the informed-consent discussion. The Investigator or appropriate site personnel must document the details of obtaining informed consent in the subject's study documents.

The subject's study partner/caregiver must also indicate their understanding of the study and their role as a study partner/caregiver to the subject during the study. The subject's study partner/caregiver must provide written consent prior to any screening visit procedures being performed indicating their agreement to participate in the study in the study partner/caregiver role.

Records related to a study subject's participation will be maintained and processed according to local laws, and where applicable, the European Union General Data Protection Regulation (EU GDPR). The consent and study information documentation will include statements describing local and regional requirements concerning data privacy, and who to contact for questions.

13 PUBLICATION PLAN

All publication rights are delineated in the Clinical Study Agreement and/or other separate agreements with the Investigator and/or Institution, as applicable.

14 CONFLICT OF INTEREST POLICY

14.1 Finance, Insurance, and Indemnity

Arrangements for finance, insurance, and indemnity are delineated in the Clinical Study Agreement and/or other separate agreements with the Investigator and/or Institution, as applicable.

16 APPENDICES

Appendix A Prohibited and Restricted Medications

Subjects taking prohibited medications at study entry will not be eligible for the study.

Subjects who require current treatment with a prohibited medication will be withdrawn from the study.

Subjects who have previously taken a prohibited medication during the study will be withdrawn from the study unless:

- the prohibited medication has been discontinued AND
- withdrawal from the study presents an unacceptable medical risk to the subject

The justification to allow the subject to continue in the trial will be made by the Sponsor/Medical Monitor with medical input from the Investigator, and will be documented. If allowed to remain in the trial, this will be reported as a major protocol deviation and not a waiver.

The table below lists prohibitions and restrictions by medication class, including representative medications within class. A **prohibited** medication is not allowed. A **restricted** medication is allowed only under certain conditions.

Medication Class	Medication ^a	Prohibition/restrictions
Adenosine receptor antagonists	PROHIBITED 
• istradefylline	
• Must be washed out at least 5 half-lives prior to Baseline
Antipsychotics other than pimavanserin	PROHIBITED All in class	
• Must be washed out 1 month or 5 half-lives (whichever is longer) prior to Baseline• Prohibited throughout the study until completion of the EOT visit
Anticholinergics	PROHIBITED 
• Centrally acting anticholinergics
○ benztropine○ biperiden○ trihexiphenidyl○ oral diphenhydramine	Anticholinergic medications whose primary mechanism of action is centrally acting are prohibited and must be washed out and discontinued at least 2 weeks or 5 half-lives (whichever is longer) prior to Baseline
	UNRESTRICTED 
• peripherally acting anticholinergics• topical diphenhydramine	Oxybutynin and other anticholinergics may be used if dose unchanged for at least 4 weeks prior to Baseline and dose is expected to remain unchanged throughout the study until completion of the EOT visit.

Medication Class	Medication ^a	Prohibition/restrictions
Anticonvulsant and mood stabilizers	PROHIBITED 
 carbamazepine lamotrigine lithium phenytoin 	
 Must be washed out 5 half-lives prior to Baseline Prohibited throughout the study until completion of the EOT visit
	RESTRICTED 
 valproate 	Valproate may be used if dose unchanged for at least 4 weeks prior to Baseline and dose is expected to remain unchanged until completion of the EOT visit.
Antidepressants	PROHIBITED 
 mirtazapine nefazadone fluvoxamine mianserin trazodone amitriptyline nortriptyline imipramine trimipramine desipramine clomipramine esketamine ketamine 	
 Prohibited throughout the study until completion of the EOT visit Must be discontinued at least 2 weeks or 5 half-lives (whichever is longer) prior to the Baseline visit
	RESTRICTED 
 citalopram escitalopram venlafaxine 	
 If subject is remaining on these medications, the dose of the permitted antidepressants on the left must be unchanged for at least 4 weeks prior to Baseline and is expected to remain unchanged until completion of the EOT visit. If the medication is being discontinued, it must be discontinued at least 2 weeks or 5 half-lives (whichever is longer) prior to the Baseline visit. 
 Citalopram is restricted to a maximum dose of 20 mg/day. Escitalopram is restricted to a maximum dose of 10 mg/day. Venlafaxine is restricted to a maximum dose of 225 mg/day
Anxiolytics	PROHIBITED 
 chlordiazepoxide diazepam flurazepam 	Prohibited at Baseline and throughout the study until completion of the EOT visit

Medication Class	Medication ^a	Prohibition/restrictions
	RESTRICTED 
 alprazolam clonazepam lorazepam oxazepam temazepam midazolam triazolam 	
 Short- or medium-acting benzodiazepine may be used for acute anxiety. Reasonable efforts should be made to use minimum dose necessary for symptom management. May not be used within 12 hours prior to an assessment visit
Hypnotics and sleeping agents	PROHIBITED 
 zolpidem zopiclone eszopiclone 	Prohibited at Baseline and throughout the study until completion of the EOT visit
	RESTRICTED 
 zaleplon ramelteon 	May not be used within approximately 12 hours prior to an assessment (including assessments on handheld device and in clinic), and efforts should be made to limit agents to lowest dose for the shortest time needed.
Stimulants and wake-promoting agents	PROHIBITED 
 methylphenidate modafinil armodafinil 	Prohibited at Baseline and throughout the study until completion of the EOT visit (see Section 6.3.6 for procedures related to a positive amphetamine test at study entry)
Non-stimulant ADHD medications	PROHIBITED 
 atomoxetine 	Prohibited at Baseline and throughout the study until completion of the EOT visit
Serotonin antagonists	PROHIBITED 
 ciproheptadine 	
 Prohibited throughout the study until completion of the EOT visit Must be discontinued at least 3 weeks prior to the Baseline visit
Antiarrhythmic drugs	PROHIBITED 
 ajmaline amakalant, semantilide amiodarone bretlyium disopyramide dofetilide dronedarone flecainide ibutilide procainamide 	Prohibited at Baseline and throughout the study until completion of the EOT visit

Medication Class	Medication ^a	Prohibition/restrictions
	
 propafenone quinidine sotalol, d-sotalol 	
Opioids	PROHIBITED 
 methadone 	Prohibited at Baseline and throughout the study until completion of the EOT visit
Antimicrobials, antifungals, and antimalarials	PROHIBITED 
 clarithromycin erythromycin levofloxacin moxifloxacin pentamidine roxithromycin 	Prohibited at Baseline and throughout the study until completion of the EOT visit
	RESTRICTED 
 artenimol/piperaquine azithromycin bedaquiline ciprofloxacin gemifloxacin norfloxacin ofloxacin fluconazole telavancin telithromycin 	
 Prohibited at Baseline but may be used during the course of the study to treat a bacterial infection (e.g., urinary tract infection, respiratory infection), post-Baseline at the discretion of the Principal Investigator. The medications on the left are only allowed under the following conditions: 
 The subject has a Baseline ECG with a QTcF <425 ms IF QRS duration is <120 ms OR The subject has a QTcF <450 ms at Baseline IF QRS duration \geq120 ms

^a Medications within each class include but are not limited to the examples listed in this table.

Appendix B Prohibited and Restricted Concomitant Medications: Inhibitors and Inducers of Cytochrome P450 Enzyme 3A4

The information presented here is intended to provide guidance and does not constitute an exhaustive list of strong CYP 3A4 enzyme (CYP3A4) inhibitors and inducers. Any questions should be discussed with the Medical Monitor or appropriate designee.

Subjects who require current treatment with a prohibited medication will be withdrawn from the study.

Subjects who have previously taken a prohibited medication during the study will be withdrawn from the study unless:

- the prohibited medication has been discontinued AND
- withdrawal from the study presents an unacceptable medical risk to the subject

The justification to allow the subject to continue in the study will be made by the Sponsor/Medical Monitor with medical input from the Investigator, and will be documented. If allowed to remain in the study, this will be reported as a major protocol deviation and not a waiver.

The metabolism of pimavanserin is affected by strong CYP3A4 inhibitors, resulting in an increase in maximum plasma concentration (C_{max}) and area under the plasma concentration-time curve (AUC) of approximately 3-fold.

Strong inhibitors of CYP3A4 are to be stopped at least 7 days or 5 half-lives prior to investigational product administration, whichever is longer. Strong inducers of CYP3A4 are to be stopped 30 days or 5 half-lives prior to investigational product administration, whichever is longer. Moderate inhibitors and inducers of CYP3A4 are allowed but should be used with caution.

STRONG INHIBITORS	grapefruit juice ^a boceprevir (Victrelis [®]) clarithromycin (Biaxin [®]) cobicistat (part of Stribild [®]) conivaptan (Vaprisol [®]) fluvoxamine (Luvox [®]) indinavir (Crixivan [®]) itraconazole (Sporanox [®]) ketoconazole (Nizoral [®]) lopinavir and ritonavir (Kaletra [®]) mibepridil (Posicor [®]) nefazodone (Serzone [®]) nelfinavir (Viracept [®])	MODERATE INHIBITORS	grapefruit juice ^a amprenavir (Agenerase [®]) aprepitant (Emend [®]) atazanavir (Reyataz [®]) ciprofloxacin (Cipro [®]) darunavir/ritonavir (Prezista [®] /Ritonavir) diltiazem erythromycin (Erythrocin [®] Lactobionate) fluconazole (Diflucan [®]) fosamprenavir (Lexiva [®]) imatinib (Gleevec [®])
-------------------	--	---------------------	--

	posaconazole (Noxafil®) quinupristin (Synercid®) ritonavir (Norvir®, part of Viekira Pak™) saquinavir (Invirase®) telaprevir (Incivek®) telithromycin (Ketek®) voriconazole (Vfend®)		verapamil (Calan®)
STRONG INDUCERS	avasimibe carbamazepine (Tegretol®) phenobarbital (Luminal®, Solfoton®) phenytoin (Dilantin®) rifampin (Rifadin®, Rifadin® IV, Rimactane®) St. John's Wort	MODERATE INDUCERS	bosentan (Tracleer®) efavirenz (Sustiva®) etravirine (Intelence®) modafinil (Provigil®) nafcillin (Unipen®, Nallpen®)

^a The effect of grapefruit juice varies widely among brands and is concentration-, dose-, and preparation-dependent. Studies have shown that it can be classified as a “strong CYP3A inhibitor” when a certain preparation was used (e.g., high dose, double strength) or as a “moderate CYP3A inhibitor” when another preparation was used (e.g., low dose, single strength). (FDA Drug Development and Drug Interactions <http://www.fda.gov/Drugs/DevelopmentApprovalProcess/DevelopmentResources/DrugInteractionsLabeling/ucm093664.htm#classInhibit>).

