4.6.2.1 Permitted, Restricted, and Prohibited Medications

Prohibitions and restrictions for concomitant medications should be followed between the initial screening visit and Visit 7/EOT/ET as specified in [Appendix A](#) and [Appendix B](#). These appendices do not constitute an exhaustive list and any questions regarding prohibited and restricted medications should be discussed with the Medical Monitor or designee.

Use of medications that could interfere with study conduct or any questions regarding prohibited and restricted concomitant medications should be reviewed and/or discussed with the Medical Monitor or designee.

Medications that can prolong QT interval are prohibited (or restricted if approved by the Medical Monitor) as specified in [Appendix A](#).

Permitted concomitant medications should remain at a stable dose throughout the study.

If a subject is on a medication restricted by the protocol, the medication should be adjusted if it is determined by the Investigator to be clinically appropriate (e.g., if the subject's symptoms are not well-controlled or if the subject cannot tolerate the current medication) in consultation with the treating physician.

Subjects who require current treatment with a prohibited medication will be withdrawn from the study.

Subjects who have taken a prohibited medication during the study will be withdrawn from the study unless:

- the prohibited medication has been discontinued, AND
- withdrawal from the study presents an unacceptable medical risk to the subject

The justification to allow the subject who has taken a prohibited medication to continue in the trial will be made by the Sponsor/Medical Monitor, with medical input from the Investigator, and will be documented. If a subject is allowed to remain in the trial, this will be reported as a major protocol deviation and not a waiver.

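### Appendix A permits telithromycin after Baseline although Appendix B classes it as a strong CYP3A4 inhibitor; it should move to the prohibited list (minor safety-text correction)

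*Protocol*

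**What the plan says.** **Appendix A, antimicrobials, restricted list.** The list ends "fluconazole telavancin telithromycin". The rule for the row is "Prohibited at Baseline but may be used during the course of the study to treat a bacterial infection", with the decision left to the Principal Investigator. The subject must also have a Baseline QTcF below 425 ms if QRS is under 120 ms, or below 450 ms if QRS is 120 ms or more. The row mentions neither CYP3A4 nor Appendix B.

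**Appendix B.** Telithromycin is in the strong-inhibitor list. The text explains why the class matters: "The metabolism of pimavanserin is affected by strong CYP3A4 inhibitors", with Cmax and AUC rising about 3-fold. It then gives three rules:
- For strong inhibitors, the rule is a washout: "Strong inhibitors of CYP3A4 are to be stopped at least 7 days or 5 half-lives prior to investigational product administration, whichever is longer".
- Strong inducers have a longer washout before the first dose, with a minimum of 30 days.
- For the weaker agents, the wording is permissive: "Moderate inhibitors and inducers of CYP3A4 are allowed but should be used with caution".

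**Section 4.6.2.1.** Both lists apply for the same period: "Prohibitions and restrictions for concomitant medications should be followed between the initial screening visit and Visit 7/EOT/ET as specified in" Appendices A and B. The section refers questions to the Medical Monitor and requires Medical Monitor approval for restricted use of QT-prolonging drugs. It does not say which appendix prevails when they differ on a drug.

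**The concern.** An investigator treating a bacterial infection would naturally look at the antimicrobial row of Appendix A. There the investigator finds telithromycin by name, an express permission and a QTcF condition to check. Nothing in the row points to Appendix B, where the same drug is in the class that the protocol wants stopped before pimavanserin starts.

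Two things are at stake:
- **Safety.** Section 1.3.1 names a potential QT-prolongation risk for pimavanserin, with an average of about 5 to 8 ms at 34 mg in the Phase 3 programme. The row's QTcF check uses the Baseline value. The first dose is taken the morning after the Baseline visit, so that value cannot reflect pimavanserin exposure at all, still less a later rise caused by an inhibitor.
- **Conduct.** Section 4.6.2.1 and both appendices call for withdrawal after a prohibited medication, or in narrow circumstances continuation recorded as a major deviation. Two sites could classify the same course of telithromycin differently, each with text to support it.

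**Working it through.** The plan gives no figure to reproduce here. The check is a comparison of the drugs named in the two appendices.

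**Step 1. Strong CYP3A4 agents in Appendix B that Appendix A also names.**

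| Agent | Appendix B | Appendix A |
|---|---|---|
| Clarithromycin | Strong inhibitor | Prohibited (antimicrobials) |
| Fluvoxamine | Strong inhibitor | Prohibited (antidepressants) |
| Nefazodone | Strong inhibitor | Prohibited (antidepressants, spelled nefazadone) |
| Telithromycin | Strong inhibitor | **Restricted** (antimicrobials) |
| Carbamazepine | Strong inducer | Prohibited (anticonvulsants) |
| Phenytoin | Strong inducer | Prohibited (anticonvulsants) |

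Inhibitors: 3 prohibited + 1 restricted = 4. Inducers: 2 prohibited. Total: 4 + 2 = 6, of which 3 + 2 = 5 are prohibited and 1 is restricted.

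**Step 2. The restricted antimicrobial row, checked against Appendix B.** It names 10 drugs. One is strong in Appendix B (telithromycin). Two are moderate (ciprofloxacin and fluconazole), which agrees with the rule that moderate agents may be used with caution. The other 10 − 1 − 2 = 7 are not listed in Appendix B. Telithromycin is therefore the only entry in the row at odds with Appendix B.

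**Step 3. Does Appendix B bar strong inhibitors on treatment?** Not in so many words. It requires them to be stopped before dosing, says only of moderate agents that they are allowed, carries a title covering prohibited and restricted medications, and repeats the withdrawal rule. Section 4.6.2.1 extends the appendices to the end of treatment. Together these imply a bar on treatment. No sentence states one.

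**Step 4. What limits the risk if a site follows the Appendix A row?**
- Section 4.6.2: apart from emergencies, subjects are to take no medication without first consulting the Investigator. That leads to the person to whom the row gives the decision.
- Section 4.6.2.1 and the opening of Appendix B: questions go to the Medical Monitor, and Section 4.6.2.1 adds the approval requirement for QT-prolonging drugs. An investigator who reads an express permission may see no question to raise, and the row does not repeat the approval requirement.
- SAP Section 13.2.7: on-treatment ECGs are scheduled at Week 4 and Week 16. A short antibiotic course could fall between them, and the row asks for no extra ECG.
- Section 6.5: unscheduled safety evaluations are possible if the Investigator judges them indicated.

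These controls lower the risk. None corrects the entry.

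**The case against.** The strongest reply is that the two lists are cumulative. Section 4.6.2.1 says that both are to be followed, and the QTcF condition in Appendix A nowhere waives Appendix B. A drug must then pass both lists, and telithromycin fails the second. Other entries support this reading. Erythromycin is a moderate inhibitor and modafinil a moderate inducer in Appendix B, a class allowed with caution, yet Appendix A prohibits both. These entries make sense if the stricter list governs.

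This reading is plausible and may well be what was intended. It does not rescue the row. No text states the rule, and the cases are not symmetrical. For erythromycin and modafinil, the stricter entry is an outright prohibition by name. For telithromycin, the entry by name is the permission, and the stricter rule has to be inferred from class text in another appendix. If the stricter list does govern, Appendix A contains a permission that must not be used, and it still needs correcting.

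A reader might infer three stronger things that the documents do not support:
- **That the protocol both expressly permits and expressly forbids the drug on treatment.** The bar in Appendix B is implied only.
- **That exposure would exceed the range studied for QT.** Multiplying 3 × 34 mg gives 102 mg, above the 68 mg top dose of the thorough QT study in Section 1.3.1. That step assumes exposure proportional to dose and applies a class figure to one drug. The documents give no telithromycin figure and no QT effect at that exposure, so I give the product no weight.
- **That the efficacy results are at risk.** Nothing in the analysis depends on this row.

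**Conclusion.** The point holds as a minor correction to safety text. Appendix A expressly permits a drug that Appendix B places in a class to be stopped before dosing and, by implication, kept off treatment. Telithromycin is the only one of the six strong CYP3A4 agents named in both appendices, and the only one of the ten restricted antimicrobials, to be out of line in this way. That pattern suggests an oversight in the list more than a deliberate choice, though the documents do not say which.

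The practical size is small. I assume that use would be rare, because one drug is concerned and about 53 subjects are expected to be enrolled; the documents give no frequency. Sample size, the mFSQ model and the other planned analyses are untouched. The conclusion rests on reading Appendix B as barring strong inhibitors on treatment. If that was not intended, the protocol allows an approximately 3-fold class effect on exposure with only a pre-dose QTcF check in the row, and the text would still need attention.

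**What to change.** In the Appendix A antimicrobial row, move telithromycin from the restricted to the prohibited list, beside clarithromycin. That alone resolves the point.

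Optionally, add a sentence to Appendix B stating that strong CYP3A4 inhibitors and inducers are prohibited until the EOT visit is complete. This would write down the implied rule and cover strong agents that Appendix A does not name, such as itraconazole and ketoconazole. If it is added, it must say how grapefruit juice is handled. Appendix B lists grapefruit juice as both strong and moderate depending on preparation, so a blanket ban would bring it under the withdrawal and major-deviation rule with no way to classify it.

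The cost is one list edit, plus one sentence if the option is taken. Section 10.7 requires every protocol modification to be submitted to the IRB/EC as an amendment or a notification; a notification needs no approval. Visits, data collection, sample size and analysis do not change.
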